**6) Data and Specimen Banking\***

At the close of the study period, when all final data have been entered, a final read-only data set will be generated to document the data used for publication as well as for potential use in future research.

**7) Data Management\***

Paper forms will be used to collect consent and demographic/family history information as well as for the ASRS and ASQ assessments. Paper forms will be scanned and stored on a secure, encrypted cloud-based system (i.e., Box) and the forms will be physically stored in a locked file cabinet.

A unique subject identifier will be assigned and used for all OAE and ABR data acquisition. OAE and ABR data will be recorded on the data acquisition system, stored electronically identified by subject number only, and backed up daily to a secure computer at the University of Miami. A deidentified database (records will be identified by subject numbers only, names will not be included) containing all study data will be created and will be accessible only to authorized study personnel. Identifying information will not be included in the analyses nor released to non-study personnel. Deidentified raw OAE and ABR data will be transferred using a secured Box account to [name] at Intelligent Hearing Systems for review to assure that the data meet the required quality for the study.

Data analysis plan:

The following statistical analyses will be performed:

- 1) Analysis of variance and t-tests will be conducted to determine if there are significant differences between the ASD and control groups, sex and ear on ABR peak latency and amplitude.
- 2) Sensitivity and specificity measures will also be conducted using Receiver Operating Characteristic (ROC) curves and d-prime measures. The optimal stimulation rate for ASD detection will be determined using these measures.

Factor: Click stimulation rate (five levels): 19, 39, 61, 120, and 250 per second. The three lower rate levels were selected to replicate previous research. The upper levels were selected to obtain ABRs with discernible peaks while challenging the neural transmission of the auditory system.

Dependent Variables: Absolute peak latencies and amplitudes.

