**2) Objectives\***

The purpose of this proposal is to develop and assess the feasibility of an automated auditory brainstem response (ABR) based neurological screening device and software module that will provide early detection of increased risk for autism spectrum disorder (ASD) and other neurological conditions (e.g., speech impairment or sudden infant death syndrome (SIDS)). Recordings will be obtained at a range of stimulation rates from 19 to 250/second to determine the optimal rate to be used for newborn screening.

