Significant latency differences in the peak components of ABRs have been identified in children with ASD compared to aged matched normal children (Dabbous, 2012; Fujikawa-Brooks et al., 2010; Kwon et al., 2007; Maziade et al., 2000; Rosenhall et al., 2003; Roth et al., 2012; Russo et al., 2010; Tas et al., 2007; Thivierge et al., 1990; Wong et al., 1991). Studies have also shown that prolonged ABRs occurred in infants who later had social engagement problems (Geva et al., 2011) and repetitive behaviors (Cohen et al., 2013). More recently, Miron et al. (2015) showed that prolonged ABR occurred in young infants later diagnosed with ASD and that this prolongation, especially in wave V, was capable of accurately classifying ASD. Although the sensitivity (84% & 80%) and specificity (56% & 70%) measures for Cohen et al. (2013) and Miron et al. (2015), respectively, are encouraging, the resulting high false positive rate would be of concern for any screening tool. It is important to point out that these values were derived primarily from testing at-risk infants and that a broader study including a large number of well-babies is required to fully develop latency norms and new specificity and sensitivity measures.

There are several options to improve test sensitivity and specificity. Choosing the proper cut-off value for absolute and interpeak latency difference between normal and ASD infants are critical for optimizing any

screening tool. In addition to abnormalities in ABR latencies, studies have shown that ABR amplitudes are also abnormal in some children with ASD (Coutinho et al., 2002; N. Russo et al., 2009). Miron et al. (2015), hypothesize that predicting ASD based on both ABR amplitude and latency may be even more accurate than predicting based solely on ABR latency. Furthermore, the use of higher stimulation rates may provide an additional way to differentiate normal versus ASD infants.

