**15) Local Number of Subjects**

100 children 1.5-5.5 years of age will be recruited to participate in the study, including 50 children with ASD and 50 age and gender-matched controls. Additional subjects will be recruited as needed to achieve a complete age and gender matched control group and to accommodate for subjects who did not fully complete the session.

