Title:

Screening for Autism Spectrum Disorders Using Auditory Brainstem Responses

Number: NCT03971578

Date: May 30, 2019

Project Funded by NIH NIDCD SBIR Grant R43DC018430-01 to Intelligent Hearing Systems Corp.

Grant Title:

Screening Device for Autism Spectrum Disorders using High Stimulation Rate ABR with Continuous Loop Averaging Deconvolution

Statistical Analysis Plan

Hypothesis: The detection of neurological anomalies can be accentuated by increasing the physiological demand on neural pathways by increasing the stimulation rate (Fujikawa-Brooks et al., 2010) and therefore increasing the specificity and sensitivity of ABR testing for ASD screening.

Rationale: The purpose of this experiment is to demonstrate that higher stimulation rates, achieved using the CLAD technique (Delgado and Ozdamar, 2004), will show differences in ABRs between age-matched populations of children with and without ASD. Although the increase in rate will also increase peak latency and decrease amplitudes, the ASD population is expected to show a greater latency shift effect and increase the specificity and sensitivity of ABR testing for ASD screening. Previously, Fujikawa-Brooks et al. (2010) used a maximum rate of 61/sec and showed a significant rate effect. Because of the time constraints of a Phase I feasibility study, testing of the target population, newborns, is not possible because a confirmed ASD diagnosis will not be available for several years. The researchers recognize that there are age related differences in ABR latencies; however, these have been well documented in a normal population. The use of an age-matched control group will provide a comparison to control for normal developmental changes in ABR latencies.

Factor: Click stimulation rate (five levels): 19, 39, 61, 120, and 250 per second. The three lower rate levels were selected to replicate previous research. The upper levels were selected to obtain ABRs with discernible peaks while challenging the neural transmission of the auditory system.

Dependent Variables: Absolute peak latencies and amplitudes, and right-left ear differences of both.

Analysis: Analysis of variance and t-tests will be conducted to determine rate effects. Sensitivity and specificity measures will also be conducted for each rate at various

References:

Delgado, R.E., Özdamar, Ö. (2004). Deconvolution of evoked responses obtained at high stimulus rates, *Journal of the Acoustical Society of America*, 115:1242–1251.

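### The best of five stimulation rates is picked from one sample of 50 + 50 children with no planned accuracy intervals, selection correction or paired accuracy comparison, so accuracy quoted uncorrected at that rate will tend to be too high

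*Protocol*

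**What the plan says.** Section 2 of the Protocol says that recordings at several rates are made "to determine the optimal rate to be used for newborn screening". Section 7 lists five rates: 19, 39, 61, 120 and 250 per second. Item 2 of its data analysis plan reads "Sensitivity and specificity measures will also be conducted using Receiver Operating Characteristic (ROC) curves and d-prime measures", followed by "The optimal stimulation rate for ASD detection will be determined using these measures". The outcomes are given as "Dependent Variables: Absolute peak latencies and amplitudes". The plan does not say which peak, or whether latency or amplitude, enters the ROC analysis. It also does not say whether the ROC curve or d-prime decides.

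Section 15 gives one sample, "including 50 children with ASD and 50 age and gender-matched controls". Further recruitment is allowed to complete the matching and replace incomplete sessions, not to validate the result.

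The SAP plans ANOVA and t-tests for rate effects, and sensitivity and specificity at each rate. That last sentence is cut off in the supplied text. The SAP's Rationale predicts that "the ASD population is expected to show a greater latency shift effect" as rate increases.

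**The concern.** When the best of several noisy accuracy estimates is picked, the winner is partly the best rate and partly the luckiest one. Its estimate in the same data is therefore biased upward. The five rates are measured in the same children, so the proper comparison between them is paired, and none is planned for accuracy. The planned ANOVA and t-tests concern mean latency and amplitude. They can address a larger latency shift in ASD, although that interaction is only implied, but they do not compare AUC, sensitivity or specificity.

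Two things are at stake: the accuracy figure carried forward for the chosen rate, and the claim that this rate is the optimum. Both bear on the stated purpose of the recordings.

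**Working it through.** The documents give no target AUC, precision or power, so there is no planned figure to reproduce.

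**Inputs from the documents.** Five rates (Protocol 7) and 50 + 50 children (Protocol 15). For a plausible level of accuracy, Protocol 3 cites "the sensitivity (84% & 80%) and specificity (56% & 70%) measures" from two earlier studies.

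**Assumptions.** Normal markers with equal SD, one marker per rate, equal correlation ρ between rates within a child (0.5, 0.7 or 0.9; the documents give none), complete data, and selection by highest AUC. The documents do not name AUC as the criterion.

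**Step 1, anchor.** d′ = z(sensitivity) + z(specificity) and AUC = Φ(d′/√2).
- 84% and 56%: d′ = 0.994 + 0.151 = 1.145, AUC 0.791.
- 80% and 70%: d′ = 0.842 + 0.524 = 1.366, AUC 0.833.

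An AUC of 0.80 is therefore a fair anchor, with 0.70 as a lower case.

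**Step 2, hand check.** The Hanley-McNeil variance is [A(1−A) + 49(Q₁−A²) + 49(Q₂−A²)]/2500, with Q₁ = A/(2−A) and Q₂ = 2A²/(1+A). At A = 0.80 this is (0.16 + 1.307 + 3.484)/2500, so SE = 0.0445 and the 95% half-width is 1.96 × 0.0445 = 0.087. The expected maximum of five independent standard normals is 1.163. If the rates are equally accurate, the winner's excess is therefore about 1.163 × SE × √(1−ρ), taking the correlation of the AUC estimates as roughly ρ:
- ρ = 0.5: 1.163 × 0.0445 × 0.707 = 0.037
- ρ = 0.7: 1.163 × 0.0445 × 0.548 = 0.028
- ρ = 0.9: 1.163 × 0.0445 × 0.316 = 0.016

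**Step 3, simulation** (6,000 replicates per setting for the first two rows), at ρ = 0.5 / 0.7 / 0.9:

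| True AUCs | Winner's AUC overstated by | Mean best-minus-worst gap |
|---|---|---|
| all five 0.70 | 0.043 / 0.036 / 0.021 | 0.089 / 0.070 / 0.041 |
| all five 0.80 | 0.037 / 0.030 / 0.018 | 0.075 / 0.059 / 0.036 |
| 250/s at 0.75, others 0.70–0.72 | 0.006–0.037 over this range of ρ | – |
| steep: 0.65, 0.65, 0.70, 0.75, 0.80 | 0.002–0.013 over this range of ρ | – |

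Repeat simulations agreed closely, giving 0.001–0.013 for the steep case. A matched-pair correlation of 0.3 moved the equal-rate figures by 0.002 or less.

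**Step 4, would an ordinary interval be enough?** Not quite. In simulation, an unadjusted 95% interval at the chosen rate covered the truth in 84–93% of trials, against 92–95% at a rate fixed in advance.

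**Step 5, can the rates be separated?** The SE of a paired difference is SE × √(2(1−r)), where r is the correlation of the two AUC estimates. Near AUC 0.80, the difference detectable with 80% power (two-sided 0.05, one unadjusted pair) is 2.80 × 0.0445 × √1.0 = 0.125 at r = 0.5, and 2.80 × 0.0445 × √0.4 = 0.079 at r = 0.8. With equal rates, the chosen rate's paired interval excluded 0 against at least one other rate in 27–34% of trials, but against all four in under 1%.

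**Step 6, cost of a wrong pick.** In the 0.75 case the chosen rate's mean true AUC is 0.731–0.744, a loss of 0.75 − 0.744 = 0.006 to 0.75 − 0.731 = 0.019.

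**The case against.** The strongest reply is that this is a Phase I feasibility study, and the Protocol's Background already says that "a broader study including a large number of well-babies is required to fully develop latency norms and new specificity and sensitivity measures". Choosing a working rate by point estimate is reasonable at this stage, and a slightly inferior choice costs little. The overstatement at AUC 0.80 (0.018–0.037) is under half the 0.087 half-width of an ordinary interval. The equal-rates case also runs against the SAP's own hypothesis, and the bias nearly vanishes if one rate dominates. All of this stands and limits the severity. It does not remove the point, because dominance is unknown beforehand and the bias has a known direction.

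A second reply concerns the text. The SAP's accuracy sentence is incomplete, and the lost words may cover thresholds or more. This also stands, so the claim is confined to the visible text. Item 2 of the Protocol's plan is complete, however, and states the selection step without a safeguard.

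A reader might infer more than the documents support:
- That only the winner's accuracy will be reported. The SAP plans sensitivity and specificity at every rate, and neither document promises a single headline figure.
- That the rates are not compared at all. They are, on mean latency and amplitude.
- That the cut-off will be tuned on the same data. The visible text does not say, and the AUC overstatement does not depend on it.
- That the design fails or needs more children. Nothing here shows that.

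**Conclusion.** The point holds as a modest reporting bias that is cheap to remove. If accuracy at the selected rate is quoted without correction, expect an AUC about 0.02–0.04 too high when the five rates are equally accurate, and about 0.01 or less when one clearly dominates. These sizes rest on normal markers, equal SDs, within-child correlation 0.5–0.9, one marker per rate and selection by highest AUC, none of which the documents specify. If latency and amplitude both competed (ten candidates, an assumption), the overstatement would be 0.043–0.068 at a true AUC of 0.70.

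It would be too strong to say that the reported accuracy is certain to be inflated. That depends on how close the rates are and on how the result is quoted. Separately, naming one optimum may not be supported, because an average gap of 0.04–0.09 between best and worst arises even among truly equal rates.

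**What to change.** Add to the SAP:

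1. Before analysis, name one primary ABR index and one measure that decides the optimal rate.
2. Add 95% intervals to the per-rate sensitivity and specificity already planned, and report AUC with intervals at all five rates. Give paired AUC differences between the chosen rate and the other four, with bootstrap intervals that resample matched sets (children within group if matching is not individual).
3. Report accuracy at the chosen rate from cross-validation that repeats the rate selection, and the cut-off selection if data-driven, in each training part. Split folds by matched set. Compare held-out cases only with held-out controls from other sets, in the same fold and at the same selected rate, then average over folds. Never pool raw values across folds that chose different rates. Latency rises with rate, and pooling biased AUC by −0.004 to −0.027 in simulation when marker means shifted 2–4 SD across rates.
4. State the group-by-rate interaction on latency as the test of the predicted greater shift in ASD.
5. A working rate may still be chosen by point estimate. Call it provisional where the paired intervals do not separate it from the other rates.

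The cost is a few lines of SAP text and some computing, with no extra children, visits or recordings. The downside is that accuracy will look less favourable and a single optimum will often not be claimable. With 250/s truly at 0.75 against 0.70–0.72, separation from all four other rates occurred in only about 2–10% of simulated trials; on the steep gradient it occurred in 14–59%.

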**8) Risks to Subjects\***

The potential risks to the subjects are minimal. The OAE and ABR equipment and procedures to be used have been used in previous studies with human subjects, with no adverse effects. The equipment is specifically designed to protect subjects from possible electric shock originating from the test equipment to the subjects and from exposure to high sound intensity levels. The device to be used has been approved by the US FDA and has passed all required IEC60601 safety tests from independent, accredited testing laboratories. The proposed testing methods have also been previously used in human clinical and research studies. There are no known side effects, risks or complications associated with the OAE and ABR assessments. Possible adverse events (AEs) may include a skin rash associated with the recording electrodes. These can be identified by skin redness or rash at the time that the electrode is removed. No serious adverse events (SAEs) are anticipated as the ABR and OAE procedures are routinely used for hearing evaluation throughout the world.

Any AE or SAE during data acquisition at the University of Miami will be reported by the University of Miami Site Director (IRB PI), [name], immediately to 1) the PI at Intelligent Hearing Systems, 2) the IRB board, 3) the study team, and 4) Independent Data Safety Monitor. The PI at Intelligent Hearing Systems will report the event within 48 hours to 5) NIH-NIDCD Staff and 6) Office of Human Research Protection.

Any adverse event associated with the data recording equipment will be handled as a device complaint by the manufacturer (Intelligent Hearing Systems) through their complaint and reporting procedure QOP-85-02-WI2 (attached). Personnel using the equipment will contact IHS immediately at [name] to report any concerns, issues or problems during the data recording process. The timeline for reporting any SAEs is outlined in the reporting procedure as mandated by the FDA.

All AEs will be reported to the Office for Human Research Protections (OHRP) in a report containing the following information:

**Name of the institution:** University of Miami

**Title of the research project:** Screening Device for Autism Spectrum Disorders using High Stimulation Rate ABR with Continuous Loop Averaging  
Deconvolution

**Grant proposal:** 1R43DC018430-01

**Grant Principal Investigator:** [name]

**Principal Investigator on IRB Protocol:** [name]

**Number of the research project assigned by the IRB:** \_\_\_\_\_ [TBD]

Explain in detail the problem that occurred

**Actions the institution is taking or plans to take to address the problem:** (e.g., revise the protocol, suspend subject enrollment, terminate the research, revise the informed consent document, inform enrolled subjects, increase monitoring of subjects, etc.).

A PDF file containing the report will be emailed to: **[contact]**

## **9) Potential Benefits to Subjects\***

A benefit to subjects will be obtaining information as to their current hearing status. Subjects will be provided with information pertaining to the OAE test results based on automated interpretation from the recording system. Subjects not passing the initial OAE screening will be informed of the test result and advised to consult their pediatrician and/or the Florida Diagnostic and Learning Resources System (FDLRS) for potential follow up. Additionally, control subjects with deviant scores on the ASRS or ASQ may be advised to consult their pediatrician and/or the Florida Diagnostic and Learning Resources System (FDLRS) for potential follow up. No other specific information will be provided to subjects. A final study report with summary data will be made available to participants upon requests and the results will also be posted at [clinicaltrials.gov](https://clinicaltrials.gov).

## **10) Vulnerable Populations\***

The primary aim of the study is to develop an improved method to screen children for ASD. As such, the use of children as subjects is critical in the assessment of the feasibility of the proposed techniques. Parents will be given the alternative to not participate in the study.

## **11) Setting**

Data collection will be conducted on the second and third floors of the Department of Psychology, Flipse Building at the University of Miami. Address: [name].

**13) Prior Approvals**

A Data and Safety Monitoring Plan was submitted to and approved by NIH.

**14) Recruitment Methods**

Recruitment will take place through the Center for Autism and Related Disabilities (CARD) and through other means such as by posting or distributing flyers at various child-friendly establishments in our community (e.g., preschools, museums, pediatrician's offices, retail businesses). The recruitment flyers are attached. Parents may contact the study investigators at their convenience, at which point the study will be described in detail and information regarding potential participants will be obtained. This prescreening will allow the researchers to determine whether the family is eligible to participate. Only children who meet the inclusion criteria for the study will be invited to schedule a lab session.

Participants will be compensated \$50 at the completion of the study. Partial compensation will be made for participants who begin but do not complete the study. Participants will be paid through ClinCard (a reloadable debit card for research studies) or through check. The ClinCard is the preferred method of paying research participants for their participation, and is managed by the Office of Research Administration (ORA). Participants will complete and sign a payment form, with their full name, date of birth, and address, in order to receive payment for participation. This information will not be linked to any of the study data and will only be used for payment purposes.

**15) Local Number of Subjects**

100 children 1.5-5.5 years of age will be recruited to participate in the study, including 50 children with ASD and 50 age and gender-matched controls. Additional subjects will be recruited as needed to achieve a complete age and gender matched control group and to accommodate for subjects who did not fully complete the session.

**16) Confidentiality**

Paper forms used to collect consent and demographic/family history information as well as for the ASRS and ASQ assessments will be scanned and stored on a secure, encrypted cloud-based system (i.e., Box) and the forms will be physically stored in a locked file cabinet. OAE and ABR data will be recorded on the data acquisition system, stored electronically identified by subject number only, and backed up daily to a secure computer at the University of Miami. Deidentified raw OAE and ABR data will be transferred using a secured Box account to Dr.

[name] at Intelligent Hearing Systems for review to assure that the data meet the required quality for the study. A deidentified database (records will be identified by subject numbers only, names will not be included) containing all study data will be created and will be accessible only to authorized study personnel.

Identifying information will not be included in the analyses nor released to non-study personnel. All local computers or cloud-based storage systems (e.g., Box) used will require a password to gain access. If requested, data will be provided to NIH and authorized University of Miami employees or other agents for the purposes of official audits or reviews.

